4.3 Statistical hypotheses

The trial is an exploratory one, and there are no null hypotheses to be tested.

5 Study design

An open-label, dual-centre, Phase 2a study to evaluate the safety, tolerability, and PD effects of a single intranasal dose of BPL-003 combined with relapse prevention psychotherapy to assess the treatment model and explore the potential effects on alcohol use and related symptoms. This study will assess a dry powder nasal spray formulation of 5-MeO-DMT benzoate (BPL-003). Enrolment of up to 12 patients with AUD is planned in up to 2 cohorts (Cohorts 1 and 2).

Patients will receive a single dose of 10 mg (Cohort 1) or 12 mg (Cohort 2) BPL-003. The doses selected for this study are based on a review of safety, tolerability, pharmacokinetic (PK), and PD data from the dose levels tested to date in study BPL-003-103 (a single ascending-dose study in healthy volunteers).

After completing the screening period, those patients who are confirmed as eligible will participate in a minimum of 3 preparatory psychological support sessions over approximately 2 weeks before the BPL-003 treatment session. These sessions will be conducted by a therapist with psychedelic knowledge and an AUD therapist. The last of the 3 sessions will be conducted at the clinic where the dosing will occur so that patients can become familiar with the dosing room, clinic staff and a practice run with the nasal delivery system can be completed. Baseline assessments will be completed on the BPL-003 treatment day, before BPL-003 administration.

BPL-003 will be administered on the treatment day in accordance with established safety practices for psychedelic research. A minimum of 3 integration sessions will occur over approximately 2 weeks after the treatment session, together with AUD relapse prevention psychotherapy that will guide the patient through the 12-week postdose follow-up period.

If triggered by the sponsor, a Safety Review Committee (SRC) will decide upon continuation of the study at the 10 mg dose or escalation to 12 mg. The SRC will comprise of, as a minimum, one Investigator (or delegate), the Sponsor's medical monitor, and the Chief Medical Officer (or delegate). The SRC will review, as a minimum, safety, tolerability, PK and PD data up to Day 1 from at least 3 patients dosed with 10 mg BPL-003 in Cohort 1. The dose may be escalated to 12 mg only if the safety, tolerability, PK and PD at 10 mg are deemed acceptable by the SRC. Dose decisions will be documented before further dosing. Additional SRC meetings may be scheduled as required.

The study visits and procedures are outlined below:

- **Screening:** Patients will be screened up to 14 days before their psychedelic preparation session to confirm their eligibility for the study.
- **Abstinence:** Patients will be expected to have no HDD in the 72 hours prior to dosing, and no alcohol in the last 24 hours. If breath alcohol is not zero on dosing day, patients may reschedule once if they are deemed not to have completely relapsed; however, if they fail the second time, they will be excluded from the study.
- **Psychedelic preparation visits:** Following the initial Screening Visit, all patients will participate in 3 preparatory sessions over approximately 2 weeks before being dosed (patients should not undertake preparation sessions if intoxicated (clinical judgement to be applied whether the patient is able to absorb the information and build a therapeutic alliance). The aim will be to establish a therapeutic alliance with the therapists during the preparatory sessions so that patients will be well prepared for the BPL-003 treatment session and receive ongoing AUD relapse prevention psychotherapy.
- **Psychological change measures and semi-structured interviews (optional):** if patients consent to these optional assessments they will be required to complete psychological change questionnaires at 5 visits during the study on Days -3, 1, 7, 28 and 84, and 3 semi-structured interviews with a therapist on Days 1, 28 and 84 (as detailed in the Psychological Change Study Manual).
- **Dosing visit:** After completion of the 3 preparatory sessions, patients will attend the clinic for their dosing visit. Patients will be resident at the clinic from the morning of Day 0 (dosing day) until at least 4 hours postdose. BPL-003 will be administered to patients in the designated setting, and the therapist will remain with patients while patients are in an altered state of consciousness.
- **Qualitative interview (optional):** After return to a usual state of consciousness after dosing, and provided they consent, patients will be asked to have a one-to-one guided

qualitative interview with independent researchers trained in microphenomenology methods to discuss their psychedelic experience (as detailed in the Qualitative Interview Study Manual). This will be done either face to face at the clinic or via video call. Psychometric scales will then be administered to provide quantitative measures of the patient's psychedelic experience.

All patients will have their readiness for discharge assessed every 30 minutes starting 90 minutes after dosing before discharge on the dosing day. The earliest a patient can be discharged will be 4 h after receiving the dose.

- **Follow-up (for 12 weeks postdose):**
 - **Psychedelic integration sessions:** Patients will have at least 3 integration sessions, lasting approximately 60-90 min, over the 2 weeks following their dose to discuss their experience with the therapists.
 - **Relapse prevention psychotherapy:** Patients will have weekly sessions following the dose of BPL-003 as defined in the AUD Therapy Manual (can be either face to face or remote) with an AUD therapist.

6 Schedule of events

Please refer to Table 1 of the protocol, version 7, dated 29 August 2024

7 Planned analyses

7.1 Interim analyses

No interim analyses are planned. This is an open label study and data will be reviewed on an ongoing basis by the Sponsor. In addition, data will be reviewed by the SRC before dose escalation.

7.2 Final analysis

The database will be locked once all patients have completed the study, data have been entered, and queries resolved. The final analysis will be carried out following database lock.

8.1 Sample size assumptions

As this is a pilot study, no formal sample size determination is appropriate

9 Analysis populations

The following populations will be identified:

Safety population: All patients who received the dose of study drug

Intent-to-treat population (ITT) population: All patients who received the study drug and a PD measure is available.

Per protocol (PP) population: All patients who received study drug and a PD measure is available and not deemed to have an important major protocol deviations

PK concentration population: All subjects who received the study drug and for whom a pharmacokinetic sample has been analysed

The primary endpoint will be analysed using the safety population.

PD endpoints will be analysed using the ITT population. A sensitivity analysis using the PP population for Alcohol use, and MEQ-30 endpoints will be performed.

9.1 Analysis datasets

All analysis datasets will be based on observed data, except as outlined in Section 12.2.

10 Treatment comparisons

The treatment comparison of interest is active between ascending dose levels.

11 General considerations for data analyses

11.1 Data display treatment and other subgroup descriptors

The sort order for treatment groups will be study treatment in ascending dose order.

Listings of data will be sorted and displayed by treatment group, patient number, and also by date and time if applicable.

The treatment descriptions to be used on all tables and listings are:

Treatment Groups
10 mg BPL-003

11.2 Conventions for summary statistics and data displays

The minimum set of summary statistics for numeric variables will be: n, mean, standard deviation (SD) (or standard error), median, minimum, and maximum. 95% confidence intervals (CI) will be presented where appropriate for data interpretation.

Categorical data will be summarised in frequency tables with n and percentage. Summaries of a categorical variable will include all recorded values.

The minimum and maximum values will be presented with the same number of decimal places as the raw data collected on the case report form (CRF) (or to 3 significant figures for derived parameters less than 100 and as integers for values more than 99). The mean and percentiles (eg median) will be presented using one additional decimal place. The standard deviation and standard error will be presented using two additional decimal places.

12 Data handling conventions

12.1 Premature withdrawal and missing data

All patients who withdraw prematurely from the study or study drug will be included in the statistical analyses.

If a patient completes the treatment period but has missing data, then this will be made apparent in the patient listings. Missing data will not be imputed.

If the study is prematurely discontinued, all available data will be listed and a review will be carried out to assess which statistical analyses are still considered appropriate.

Data collected at unscheduled time points during the study will not be used in the summaries or data analyses. They will be included in the listings.

If time information (ie hours and/or minutes) for adverse events (AEs) or concomitant medication is missing, but the day is present, then the time will be calculated in days. If date information is partial or missing, then any derived times (eg AE start time from last study medication) will be listed as missing.

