4.2. Number of Patients

Enrolment of patients with AUD is planned until up to 12 evaluable patients in up to 2 Cohorts have completed (dosed and completed Day 0) the study. Although this study is exploratory and there is no formal sample size calculation, the sample size is estimated to be able to detect common drug-induced safety events in this patient population ([Shen, 2019](#)).

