10.1.10. Laboratory Assessments

Blood samples will be collected at the Screening Visit and at the visits outlined in [Table 1](#). Clinical laboratory evaluations will be performed locally. Additional laboratory tests should be performed per standard of care, and significant findings should be reported in the CRF.

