4.2 Study endpoint(s)

4.2.1 Primary endpoint(s)

Safety Endpoints:

- Percentage of patients with treatment-emergent adverse events (TEAEs)
- Percentage of patients with clinically significant postdose abnormal laboratory tests
- Percentage of patients with clinically significant abnormal postdose vital sign measurements (Heart rate (HR), Blood Pressure (BP), and body temperature)
- Percentage of patients with postdose suicidal ideation as determined by the Columbia-Suicide Severity Rating Scale (C-SSRS)
- Change in C-SSRS score compared to Baseline at Days 7 and 84
- Readiness for discharge questionnaire
- Measure the frequency, emotional valence and functional impact of any re-activation events in the study through the Reactivation Questionnaire (ReAQ)

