n = number of patients (patients with >1 TEAE are counted only once per system organ class and preferred term)

*Coded using MedDRA version xx.x

*Programming notes: Each preferred term counted only once across all severities for each patient
SOCs and PTs are sorted in decreasing order of frequency
Presented for all applicable MedDRA system organ classes and terms.*

Template T_AE4

Table 14.3.3.xx Summary of treatment-emergent adverse events by day of onset

System Organ Class*	Preferred Term	Day of Onset	Treatment 1 (N=xx n (%))
Nervous system disorders	Dizziness	Day 0	x (xx)
		Days 1-6	x (xx)
		>=Day 7	x (xx)
	Headache ↓	Day 0	x (xx)
		Days 1-6	x (xx)
		>=Day 7	x (xx)
Gastrointestinal disorders	Abdominal discomfort	Day 0	x (xx)
		Days 1-6	x (xx)
		>=Day 7	x (xx)

Source: Listing 16.2.xx

n = number of patients

*Coded using MedDRA version xx.x

*Programming notes: SOCs and PTs are sorted in decreasing order of frequency
Presented for all applicable MedDRA system organ classes and terms.*

Template T_LB4

Table 14.3.4.xx Summary of post dose clinically significant abnormal laboratory values by treatment and planned relative time

Laboratory Test (units)	Treatment	Planned Relative Time	Clinically Significant n (%)
Treatment 1 (N=xx)			

Source: Listing 16.2.xx

Programming notes: Continued with all tests, and time points.

Template T_LB2

Table 14.3.5.xx Summary of chemistry laboratory values

Laboratory Test (units)	Treatment	Planned Relative Time	n	Mean	SD	Median	Min	Max	Change from Baseline					
									n	Mean	SD	Median	Min	Max
									Treatment 1 (N=xx)					

Source: Listing 16.2.xx

Programming notes: Continued with all time points

Template T_VS1

Table 14.3.6.xx Summary of vital signs

									Change from Baseline					
Variable (units)	Treatment	Planned		Mean	SD	Median	Min	Max						
		Relative Time	n						n	Mean	SD	Median	Min	Max
Systolic Blood Pressure (mmHg)	Treatment 1 (N=xx)													

Source: Listing 16.2.xx

Programming notes: Continued with all variables, and time points

Template T_VS2

Table 14.3.6.xx Summary of vital signs of potential clinical importance

Treatment	Planned Relative Time	Systolic Blood Pressure (mmHg)		Diastolic Blood Pressure (mmHg)		Heart Rate (beats/min)		Temperature (C)		etc	
		n	(%)	n	(%)	n	(%)	n	(%)	n	(%)
Treatment 1 (N=xx)	Time 1										
	Time 2										

Source: Listing 16.2.xx

Programming notes: Continued with all parameters. n = total number of results for that parameter

Template T_VS3

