Table 14.3.6.xx Summary of vital signs of potential clinical importance by parameter and treatment (excluding baseline time point)

Treatment	Systolic Blood Pressure (mmHg)		Diastolic Blood Pressure (mmHg)		Heart Rate (beats/min)		Temperature (C)		etc		Overall*	
	n	(%)	n	(%)	n	(%)	n	(%)	n	(%)	n	(%)
Treatment 1 (N=xx)												

Source: Listing 16.2.xx

Patients only counted once per parameter

*Patients only counted once per treatment

Programming notes: Continued with all parameters. n = total number of results for that parameter
Only include post-treatment time points

Template T_VS4

Table 14.3.6.xx Summary of post dose clinically significant vital signs

Treatment	Planned Relative Time	Clinically Significant	
		n	(%)
Treatment 1 (N=xx)	Time 1 Time 2		

Programming notes: Continued with all timepoints. n = total number of results for that parameter

Template T_VS5

Table 14.3.7.xx Summary of peak Vital Signs ranges by treatment, ranges and parameter - Day 0 post dose

	Systolic Blood Pressure (mm Hg)										
	<130	130 - 139	140 – 149	150 – 159	160 – 169 n	170 – 179	180 – 189	190 – 199	200 - 209	210 – 219	> =220
Treatment	n (%)	n (%)	n (%)	n (%)	(%)	n (%)	n (%)	n (%)	n (%)	n (%)	n (%)
Treatment 1 (N=xx)											

Source: Listing 16.2.xx

The maximum value across all time points per subject is used for analysis.

Programming notes: Continued with all variables . n = total number of results for that parameter.
Continued with all the ranges in **section 14.8.1**

Template T_VS6

Table 14.3.6.xx Summary of peak vital signs by treatment and parameter - baseline and Day 0 post dose

Variable (units)	Treatment	Planned Relative Time	n	Mean	SD	Median	Min	Max
Systolic Blood Pressure (mmHg)	Treatment 1 (N=xx)	Predose Day 0, Postdose						

Source: Listing 16.2.xx

Programming notes: Continued with DBP and HR. The maximum value across all time points per subject are used for analysis.

Template T_EG2

Table 14.3.7.xx Summary of ECG values

Variable (units)	Treatment	Planned Relative							Change from Baseline					
		Time	n	Mean	SD	Median	Min	Max	n	Mean	SD	Median	Min	Max
Heart Rate (bpm)	Treatment 1 (N=xx)													
PR Interval (msec)	Treatment 1 (N=xx)													

Source: Listing 16.2.xx

Programming notes: Continued with all time points
Do not summarise RR or QRS axis

Template T_EG3

Table 14.3.7.xx Summary of QTcF values and changes in QTcF values of potential clinical importance

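### No planned table gives the two primary percentages of patients with a clinically significant laboratory or vital-sign abnormality, and unscheduled values are left out of the summaries

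*SAP*

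**What the plan says.** SAP 4.2.1, like Protocol 3.1, sets two primary safety endpoints whose unit is the patient: "Percentage of patients with clinically significant postdose abnormal laboratory tests" and "Percentage of patients with clinically significant abnormal postdose vital sign measurements". SAP 9 assigns the primary endpoint to the Safety population.

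The planned displays are in SAP 19.1 and 19.2.1:

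- **Laboratory:** Table 14.3.4.1, template T_LB4, titled "Summary of post dose clinically significant abnormal laboratory values by treatment and planned relative time". It has one row per test and planned time.
- **Vital signs:** Table 14.3.6.4, template T_VS4. It has one row per planned time and no column for the parameter, and its note reads "Continued with all timepoints. n = total number of results for that parameter".
- **Potentially clinically important (PCI) vital signs:** template T_VS3 pools the postdose time points and counts each patient once. PCI status comes from the fixed ranges in SAP 12.4, whereas clinical significance is the investigator's judgement (SAP 14.8.1).

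SAP 14.7 and 14.8.1 promise frequencies of clinically significant values without naming the counting unit.

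On unscheduled data, SAP 12.1 says: "Data collected at unscheduled time points during the study will not be used in the summaries or data analyses". The next sentence keeps those values in the listings. Protocol 10.1.10 expects some to arise: "Additional laboratory tests should be performed per standard of care, and significant findings should be reported in the CRF".

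The heart-rate bands for the Day 0 peak in SAP 14.8.1 run up to 110–119 and resume above 120.

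**The concern.** A primary endpoint should come out of the analysis as the plan is written. Here a programmer who follows the templates produces a set of by-time counts, and the percentage of patients with any abnormality must be worked out by some other route. No single row is the endpoint, and adding rows counts a patient again at each time point where the abnormality recurs.

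The unscheduled-data rule bears on the same two endpoints. An additional laboratory test is often done because something looks wrong, so barring such results from all summaries can remove the very value that makes a patient a case. With at most 12 patients, one patient moves the percentage visibly.

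**Working it through.** **1. Is there a figure to reproduce?** No. The SAP states no hypothesis (4.3), no sample-size calculation (8.1) and no expected event rate. The check is whether the planned rows determine the endpoint.

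**2. Endpoint against display**

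| Quantity | Split by planned time | Any postdose time, patient counted once |
|---|---|---|
| Clinically significant laboratory values (primary) | Yes, T_LB4 | None |
| Clinically significant vital signs (primary) | Yes, T_VS4 | None |
| PCI vital signs (not the endpoint) | Yes, T_VS2 | Yes, T_VS3 |
| TEAEs (primary) | By day of onset, T_AE4 | Yes, T_AE1 and T_AE2 |

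**3. What the rows allow.** Inputs:
- N = 12, the planned maximum (SAP 5), with every patient assumed to have data at every time point.
- Postdose laboratory visits: Days 1, 28 and 84 (Protocol Table 1), so k = 3.
- Postdose vital-sign times: 10, 20, 30, 40 and 60 minutes, then every 30 minutes to 4 hours. That is 5 + 6 = 11 on Day 0. With Days 1 and 84, k = 13.

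If each of k rows shows 1 patient of N, the any-time count lies between 1 (the same patient throughout) and min(k, N) (as many different patients as possible).

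- One laboratory test: 1 to 3 patients, so 1/12 = 8.3% to 3/12 = 25.0%.
- Vital signs: 1 to 12 patients, so 8.3% to 100%. Adding the rows gives 13/12 = 108.3%, which is impossible as a percentage of patients.

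T_LB4 is also split by test, so the percentage of patients with an abnormality in *any* test is determined even less.

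**4. Typical gap between a row and the endpoint.** Suppose each patient has the same rate p at each time point, independently across times. The any-time rate is 1 − (1 − p)^k. The values of p are assumptions.

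| p per time point | Laboratory, k = 3 | Vital signs, k = 13 |
|---|---|---|
| 5% | 14.3% | 48.7% |
| 10% | 27.1% | 74.6% |
| 20% | 48.8% | 94.5% |

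Repeated readings in one patient are likely to be correlated, so these lie at the upper end.

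**5. Effect of the unscheduled-data rule.** Each patient whose only clinically significant value is unscheduled lowers the percentage by 1/12 = 8.3 points. With an assumed N of 6 the step is 1/6 = 16.7 points.

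**6. Which values the rule can remove**
- *Additional laboratory tests* (Protocol 10.1.10): a clear case. If the finding appears only there, it is outside T_LB4.
- *Repeat of an out-of-range postdose laboratory test:* not lost. SAP 12.2 keeps the out-of-range value in the summary, not the repeat.
- *Blood-pressure repeat after a systolic reading above 160 mmHg* (Protocol 10.1.2): the planned reading that triggered it remains.
- *Assessments at early withdrawal* (Protocol 5.3): unclear. SAP 12.1 includes withdrawn patients and SAP 12.3 defines no windows. Nothing says whether these assessments count as the final visit or as unscheduled.

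**7. Heart-rate bands.** The last two are 110–119 and >120, so a peak of exactly 120 belongs to neither. The top blood-pressure bands use ≥ and have no such gap.

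**The case against.** The strongest reply is that nothing is lost. Unscheduled values are listed, and Listings 16.2.8.1, 16.2.8.3, 16.2.8.5 and 16.2.9.2 show clinically significant values by patient. With 12 patients the count can be made by hand. This is correct, and it makes the matter one of summarisation. It does not excuse a primary endpoint with no programmed result.

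A second reply concerns laboratory tests. Protocol 10.1.10.3 requires every clinically significant result to go on the adverse-event page, whenever it was found, so postdose cases should reach the per-patient TEAE tables. This stands and reduces the laboratory risk, but the TEAE percentage pools all events and is not the laboratory endpoint. For objective findings generally, Protocol 10.2.1.1 says only that they may be considered adverse events, so vital signs are less protected.

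Four stronger readings are tempting but not supported:

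- *The percentages are biased low.* Splitting by time does not itself bias anything: one row can understate the any-time figure and a sum of rows can overstate it. Under-counting needs a patient whose only clinically significant value was unscheduled.
- *Unscheduled data are discarded.* They are excluded from summaries and kept in listings.
- *T_VS4 counts results, not patients.* Its note suggests this, but the same note appears in T_VS3, whose footnote counts each patient once. The unit is unclear.
- *Twelve patients cannot support the Protocol 4.2 statement that* "the sample size is estimated to be able to detect common drug-induced safety events in this patient population". The chance of at least one case, 1 − (1 − p)^12, is 46% at 5% incidence, 72% at 10% and 93% at 20%. The answer depends on what *common* means, which the documents do not define, and the same section disclaims a formal calculation.

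**Conclusion.** The point holds in a limited form. As written, the plan does not produce two of its primary percentages, because neither T_LB4 nor T_VS4 has an any-time patient row and T_VS3 covers a different quantity. This follows from the templates and needs no assumption. The size is illustrative: at N = 12, identical rows of 1/12 fit 8.3% to 25.0% of patients for one laboratory test and 8.3% to 100% for vital signs.

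The second part is conditional. A patient is missed only if the sole clinically significant value was unscheduled, at a cost of 8.3 points each. The documents give no rate for this, so the expected loss cannot be stated. It should be smaller for laboratory tests than for vital signs.

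The heart-rate gap is certain but minor. It affects a descriptive table that does not report a primary endpoint.

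**What to change.** 1. **SAP 12.1:** limit the exclusion of unscheduled values to by-visit summaries. Pooled postdose counts and Day 0 peaks would then use all postdose values, scheduled or not; SAP 14.8.1 already defines the peak as the maximum over all time points.
2. **T_LB4 and T_VS4:** add a row *any postdose time* giving n/N (%) of Safety-population patients with at least one clinically significant value, scheduled or unscheduled, each patient counted once. In T_LB4 the row should pool all tests, and in T_VS4 all parameters, because that is how the endpoints are worded.
3. **Precision:** preferably give an exact 95% confidence interval with that row. SAP 11.2 already allows intervals where they help interpretation. For 0/12 the upper limit is 1 − 0.025^(1/12) = 26.5%, useful context for a null count.
4. **SAP 14.8.1:** change the top heart-rate band from >120 to ≥120.

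The cost is a few lines of SAP text, one row in each of two tables and a small programming change. No new data are collected. The changes should be made before database lock.
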